#### 3) Local Versus Central Review

An independent photographic review committee, with access to de-identified digital medical photography results and biopsy results, may be installed by the sponsor upon emerging results. As such, independent photographic reviews will not be "real-time". Clinical management decisions generally will be as per investigator response assessments and local pathology review. In case an independent photographic review committee will be installed during ongoing treatment of patients in the study, and in the unlikely event that independent review yields major differences with the local response assessment that could have implications for the ongoing management of an active patient on study, the situation will be discussed between the sponsor and the investigator in order to determine patient management.

#### 4) Confirmation of Responses

After any observation of an objective response (i.e., CR/iCR, PR/iPR), confirmatory digital standardized medical photography (and radiologic imaging, if performed as part of the initial response assessment) will be obtained ≥4 weeks following initial documentation of objective response. For any complete responses observed in digital medical photography of externally visible target lesions, confirmatory biopsies are required to establish status of CR/iCR.

#### 5) Metastatic cSCC Patients with Externally Visible Tumors

Externally visible tumors will generally be followed by RECIST v1.1 and iRECIST criteria. It is possible that some patients with metastatic cSCC may also have externally visible lesions that are measurable by digital medical photography. In such circumstances, the externally visible lesions generally will be followed as nontarget lesions. The exception to this rule would be a patient with externally visible lesions in whom the only M1 lesions are not measurable by RECIST (e.g., a patient with bone-only metastases), in which case the externally visible lesions (lesion size ≥10 mm in baseline dimensional perpendicular axes) would be target lesions and followed as per clinical response criteria in this appendix, and the -non-measurable metastatic lesions (e.g., bone metastases) would be followed as non-target lesions. For any target lesions that are measured by digital medical photography, measurements will be bi-dimensional.

#### 6) Patients with Deeply Invasive Tumors

Tumor measurements for these patients will generally be performed with digital medical photography (bi-dimensional measurements). However, some patients may have deeply invasive target lesions in which tumor measurements can better be obtained with cross-sectional imaging (e.g., MRI with gadolinium or CT with contrast). For any target lesions that are measured by cross-sectional imaging (MRI gadolinium or CT with contrast), measurements will uni-dimensional according to RECIST v1.1.

Clinical Response Criteria for Externally Visible Tumors (for patients with locally advanced cSCC, and patients with metastatic cSCC in which target lesions are followed by digital medical photography)

#### **B. New Lesions**

A new cutaneous lesion consistent with cSCC will be considered as clinical PD if the lesion is ≥10 mm in both maximal perpendicular diameters and can be clearly documented as not being previously present, unless it is confirmed on biopsy not to be consistent with cSCC. If a new cutaneous lesion is not biopsied or if the histology is inconclusive, it should be considered cSCC and deemed clinical PD.

# Overall Clinical Responses for Locally Advanced cSCC Lesions That are Measured by Digital Medical Photography

Externally Visible Tumor Dimension a	New Lesions a	Clinical Response
CR of externally visible disease	No	Clinical CR b
PR of externally visible disease	No	Clinical PR
SD of externally visible disease	No	Clinical SD
PD of externally visible disease	Yes or No	Clinical PD
Any	Yes	Clinical PD

CR=complete response; PD=progressive disease; PR=partial response; SD=stable disease

## **Composite Response Criteria**

These criteria are for patients who have locally advanced or metastatic cSCC that is measurable by BOTH clinical response criteria by digital medical photography and RECIST v1.1 using radiologic imaging.

a See above for definitions.

b Negative biopsy showing no residual malignant cells is required for any lesion be deemed clinical CR.

The "Clinical Response" column in this table will be based on the results of the "Clinical Response" (far-right) column of the table above.

Clinical Response (Digital	RECIST v1.1 Response	Composite (Overall):
Medical Photography)	(Radiology)	Clinical + RECIST Response
clinical CR	CR or NA	CR
NA	CR	CR
clinical CR	PR or SD	PR
clinical PR	CR, PR, or SD, or NA	PR
NA	PR	PR
clinical SD	CR or PR	PR
clinical SD	SD or NA	SD
NA	SD	SD
clinical PD	Any	PD
Any	PD	PD

CR=complete response; NA="not applicable" (e.g., assessment not done); PD=progressive disease; PR=partial response; SD=stable disease.

In addition, if all previously inoperable target lesions are rendered operable with clear margins obtained at the time of surgery, this will be considered a PR. If the investigator deems a previously unresectable lesion to be potentially resectable, due to response to study treatment, the medical monitor should be consulted prior to any surgical procedure being performed. A decision will be rendered by the sponsor as to whether the planned surgical intervention is compatible with study requirements. (This statement does not apply to patients in emergency life-threatening situations that require immediate surgery).

Note: If composite (overall) response evaluation of PD emerges for the first time, iRECIST assessment criteria for new lesion documentation apply (see Appendix 4) and the investigator will assess the clinical status of the patient in case pseudo-progression is suspected.

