# 8.2.1. Imaging Requirements

Medical photography and computed tomography (CT) or magnetic resonance imaging (MRI) for tumor assessment will be performed locally at each scheduled tumor assessment time point (after every cycle), and at any time when disease progression is suspected.

Note: after a response evaluation of PD/iCPD while on study treatment, additional scans are not required at scheduled follow-up visit procedures.

The choice of whether the imaging is by CT or MRI is an investigator decision (see Appendix 3). Once the choice has been made to use CT scan or MRI, subsequent assessments should be made using the same modality whenever possible.

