# COMPOSITE RESPONSE CRITERIA FOR PATIENTS WITH LOCALLY ADVANCED cSCC

This appendix describes clinical response criteria for externally visible lesions that can be measured bi-dimensionally using digital medical photography. This appendix also provides composite response criteria for disease that is measurable by both clinical response criteria and RECIST v1.1.

Radiologic imaging (preferably, MRI with gadolinium) will be essential in the evaluation of tumors that have subdermal components that cannot be adequately assessed by digital medical photography.

Response assessments occur after every cycle. Standardized digital photographs of the externally visible component of all target lesions must be obtained at baseline and at the time of each subsequent tumor assessment. Guidelines for digital medical photography will be provided to the sites. Investigators will also provide a clinical description of the externally visible target lesion(s) at baseline and at each tumor assessment, as well as comments on any changes in the lesion(s) since the previous assessment.

a In exceptional circumstances, unequivocal progression in non-target lesions may be accepted as PD.

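### The composite response table credits CR or PR when one of two required assessments was not done, so a visit that would have been PD can be recorded as a response

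*Combined protocol and SAP*

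**What the plan says.** The Composite Response Criteria in Appendix 3 are for patients whose disease is "measurable by BOTH clinical response criteria by digital medical photography and RECIST v1.1 using radiologic imaging". The table combines a photographic (clinical) result with a radiologic one. Its footnote expands NA as not applicable and gives "e.g., assessment not done" as the example. Four combinations credit a response with one method absent:

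- clinical CR + NA = CR
- clinical PR + NA = PR (the radiology cell reads "CR, PR, or SD, or NA")
- NA + CR = CR
- NA + PR = PR

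PD by either method overrides everything else. The table has no not-evaluable row, although Appendix 4 lists not evaluable among the possible outcomes.

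The surrounding rules are these:

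- **Section 8.2.1:** photography and CT or MRI "will be performed locally at each scheduled tumor assessment time point". No consequence is given for a missed method.
- **Table 1, footnote 4:** imaging is also done when a CR is confirmed, using the baseline technique.
- **Appendix 3, Confirmation of Responses:** photography is repeated after at least 4 weeks, with "radiologic imaging, if performed as part of the initial response assessment".
- **Appendix 3, opening of the composite section:** radiology "will be essential in the evaluation of tumors that have subdermal components" that photographs cannot adequately assess.
- **Sections 5.2.1 and 5.2.2.2:** the Stage 1 decision needs no confirmation of response.
- **Section 10.3.1:** the non-responder rule covers four reasons for discontinuation and is silent on a missed method.

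**The concern.** Where both methods apply, a result from one describes only part of the disease. Photographs cannot show a new visceral lesion, and a scan may not show a new skin lesion. Under the table as written, leaving out a method removes its power to show PD while the other method can still earn CR or PR. Best response is the best one recorded before progression is documented (Section 8.2.2), so one such visit can make the patient a responder.

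The endpoint is assessed by investigators in an open-label trial, and independent review is optional. One patient decides at either limit: 0 of 10 stops an arm and 1 of 10 opens Stage 2; 3 of 29 fails and 4 of 29 rejects the null.

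**Working it through.** **1. Reproduce the design (Section 10.1).** Inputs: 10 patients then 19, stop at 0 of 10, reject at more than 3 of 29, p0 = 5%, p1 = 20%.

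P(stop at p0) = 0.95^10 = 0.599.

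Type I error = Σ P(X1 = x) · P(X2 ≥ 4 − x), with X1 ~ Bin(10, 0.05) and X2 ~ Bin(19, 0.05):

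- x = 1: 0.3151 × 0.0665 = 0.0210
- x = 2: 0.0746 × 0.2453 = 0.0183
- x = 3: 0.0105 × 0.6226 = 0.0065
- x ≥ 4: 0.0010

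The sum is 0.0468. At p1 the same formula gives power 0.801, so type II error is 19.9%. Expected size at p0 is 10 + 0.401 × 19 = 17.6. All agree with the stated 4.7%, 19.9%, 59.9% and about 18.

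**2. Run the table with one method missing.** Take all 16 pairs of photographic and radiologic results (CR, PR, SD, PD) and replace each method in turn by NA, giving 32 substitutions.

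| Effect of the missing method | Cases | Which |
|---|---|---|
| Non-responder becomes responder | 4 | Clinical CR or PR with radiologic PD, scan missed; radiologic CR or PR with clinical PD, photograph missed |
| PR becomes CR, ORR unchanged | 4 | Clinical CR with radiologic PR or SD, scan missed; radiologic CR with clinical PR or SD, photograph missed |
| Responder lost (PR becomes SD) | 4 | Clinical SD with radiologic CR or PR, scan missed; radiologic SD with clinical CR or PR, photograph missed |
| PD becomes SD, ORR unchanged | 2 | SD by the method done, PD by the method missed |
| No change | 18 | The rest |

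ORR therefore gains a false responder only when the missed method would have shown PD.

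**3. Sensitivity of the type I error.** Let q be the share of true non-responders falsely credited. The documents do not give q. At a true 5% rate the observed rate is p = 0.05 + 0.95q, which goes into the formula of step 1. No allowance is made for lost responders.

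| q (assumed) | Observed rate | Stop after Stage 1 | Type I error |
|---|---|---|---|
| 0 | 5.00% | 59.9% | 4.7% |
| 0.25% | 5.24% | 58.4% | 5.4% |
| 0.5% | 5.48% | 56.9% | 6.1% |
| 1% | 5.95% | 54.1% | 7.8% |
| 2% | 6.90% | 48.9% | 11.8% |

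The first two non-zero rows correspond, for illustration, to 50% of patients measurable by both methods × 5% to 10% with CR or PR on one method and PD on the other × 10% with that other method missed = 0.25% to 0.5%. All three factors are assumptions.

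**The case against.** The other side has several good points.

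- **Both methods recur every cycle.** Section 8.2.1 schedules both at each assessment, and Table 1 footnote 4 adds imaging at CR confirmation. A reader might infer that radiologic disease could go without re-imaging for the whole course; that would take repeated departures from the schedule. What remains is a PR: its confirmation rule does not ask for a skipped scan to be made up, and the interim needs no confirmation.
- **Visible responses have their own safeguards.** Clinical CR needs negative biopsies on central review, and clinical CR and PR must last at least 4 weeks. These test visible disease only and cannot detect progression on a scan.
- **The effect runs both ways.** A reader might infer pure inflation of ORR. Step 2 shows four routes to losing a responder beside four to gaining one.
- **The RECIST v1.1 table is no stricter for ORR.** It caps target CR at PR when non-target lesions were not evaluated, but PR is still a response.
- **NA may have been meant for patients with disease by one method only.** Section 6.1 lets locally advanced patients qualify by either method, and deeply invasive lesions may be measured by imaging. This is plausible, but the table's stated population and its footnote example do not limit NA to such patients.
- **Section 10.3 leaves exact endpoint definitions and missing-data procedures to the SAP.** A rule there could help, and its absence cannot be asserted. It would still have to override Appendix 3, which investigators use to assign responses.

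**Conclusion.** The rule is wrong as written and should be changed. In patients for whom both methods apply, a visit with one method not done can be credited as CR or PR. No rule in the text reviewed makes that visit not evaluable, so a visit that would have been PD can enter the primary endpoint as a response.

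The size is unknown. Type I error of about 5.4% to 6.1%, or 7.8% to 11.8% at the higher assumed rates, is a sensitivity range. It rests on assumed values of q, independence between patients and no offset from lost responders.

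A reader might also quote the error given that one false responder has certainly occurred: 16.3% if in Stage 1 (at least 3 of the other 28 respond) or 12.8% if in Stage 2. Those figures show how sensitive a 10/29 design is to any misread, whatever its cause, and do not estimate the effect of this table. The documents do not support a claim of material inflation, only that the rule permits error in either direction where one patient can decide.

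**What to change.** In Appendix 3 and the SAP:

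1. Split NA in two. 'Not applicable: no disease by this method at baseline' keeps the current rows. 'Not done', for a method used at baseline, makes the composite not evaluable for CR, PR or SD at that visit, unless the performed method shows PD.
2. Require every method used at baseline when a CR or PR is confirmed. Reconcile the Confirmation of Responses paragraph with Table 1 footnote 4 and Section 8.2.1.
3. For the interim, before declaring 0 of 10, use the missed assessment once completed, or the next evaluable visit, for any patient lacking a method at the third assessment.

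This changes wording only; the sample size and decision limits stay as they are. Some responses will be credited at a later visit, typically one 6-week cycle. Without item 3, a method missed at the third assessment could turn a true 1 of 10 into 0 of 10 and stop an arm. With it, the interim may wait for one more assessment.

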#### C. Ulcerated Lesions

This section only pertains to target lesions that have extensive ulceration at baseline that prevents measurement by the above methods in this appendix. Response criteria are as follows:

- **CR**: Re-epithelialization of the entire baseline area of ulceration of target lesion(s), maintained over  $\geq 4$  weeks
- **PR**: There are no criteria for partial response.

- **SD:** Not meeting criteria for CR or PD
- **PD:** New ulceration of target lesion(s) not related to (i.e., in a location separate from) tissue biopsy or other known trauma, persistent without evidence of healing for  $\geq 2$  weeks

Response and progression will be evaluated in this study using the international criteria proposed by the revised RECIST v1.1 guideline (Eisenhauer et al., 2009) and according to iRECIST (Seymore et al., 2017; see Appendix 4), which introduces additional tumor assessments and evaluation criteria in situations where pseudo-progression is suspected.

# Appendix 4 iRECIST

Response and progression will be evaluated in this study using the international criteria proposed by the revised RECIST v1.1 guideline (Eisenhauer et al., 2009) and according to iRECIST (Seymore et al., 2017), which introduces additional tumor assessments and evaluation criteria in situations where pseudo-progression is suspected.

This appendix describes the iRECIST process for assessment and evaluation of disease progression.

Tumor Assessment at Screening and Prior to iRECIST Progression

At every tumor assessment, target and non-target lesions identified at baseline by RECIST v1.1 will be assessed according RECIST v1.1. Until first radiographically assessed disease progression based on RECIST v1.1, there is no distinct iRECIST assessment. Accordingly, possible response evaluation outcomes are CR, PR, SD, PD, and not evaluable.

Response Evaluation and Decision at RECIST v1.1 Progression

At first radiographic assessment of disease progression according to RECIST v1.1, new lesions will be classified as measurable or non-measurable, using the same size thresholds and rules as for baseline lesion assessment in RECIST v1.1. From measurable new lesions,  $\leq$ 5 lesions total ( $\leq$ 2 per organ), may be selected as New Lesions – Target. The sum of diameters of these lesions will be calculated and kept distinct from the sum of diameters for target lesions at baseline. All other new lesions will be followed qualitatively as New Lesions – Non-target.

For patients whose radiological tumor assessment show evidence of disease progression by RECIST v1.1 criteria, the investigator will decide whether to continue a patient on study treatment and repeat imaging according to iRECIST or discontinue the patient according to disease progression according to RECIST v1.1. This decision by the investigator should be based on the patient's overall clinical condition, in particular in the assessment of clinical stability.

[figure not shown]
Clinical stability is defined as the following:

- No decline in ECOG PS
- Absence of increases of clinically relevant disease-related symptoms and signs assessed to be associated with disease progression
- No requirements for intensified management of disease-related symptoms, including increased analgesia, radiation, or other palliative care

Any patient deemed **clinically unstable** should be discontinued from study treatment at site-assessed first radiologic evidence of disease progression and assigned a response evaluation of PD (according to RECIST v1.1), and it is not required to have repeat tumor imaging for confirmation of PD by iRECIST (iCPD).

If the patient is deemed to be clinically stable, and the investigator decides to continue treatment, new response categories defined by iRECIST, including iUPD and iCPD, will be used from there on (using iRECIST for patient management as shown in the figure below).

RECIST v1.1 and iRECIST: An Example of Assessment

iCR=complete response; iCPD=confirmed progression; iPR=partial response; iSD=stable disease; iUPD=unconfirmed progression; RECIST=Response Evaluation Criteria in Solid Tumors; TP=timepoint.

Note: Prefix "i" indicates immune responses assigned using iRECIST; others without "i" are confirmed by RECIST v1.1.

Source: Seymore et al., 2017

Additional imaging for confirmation should be scheduled 4 to 8 weeks from the imaging on which iUPD is seen. This may correspond to the next visit in the original visit schedule. Images should continue to be sent to the central imaging vendor for potential retrospective independent response evaluation

#### Response Evaluation After the First iUPD

The response evaluation of the subsequent confirmation imaging proceeds at scheduled visits, as before, with possible outcomes of iCPD, iUPD, and iSD/iPR/iCR, see table below.

# Example Scenarios of Assignments of Best Overall Response using iRECIST After First Diagnosis of iUPD

	Timepoint	Timepoint	Timepoint	Timepoint	Timepoint	iBOR
	response	response	response	response	response	
	n	n+1	n+2	n+3	n+4	
Example 1	iUPD	iPR, iSD, or NE	iCR	iCR	Any	iCR
Example 2	iUPD	iPR	iPR	Any except iCR	Any except iCR	iPR
Example 3	iUPD	iUPD, iSD or NE	iPR	iPR	Any except iCR	iPR
Example 4	iUPD	iSD	Any, except iPR,	Any, except iPR,	Any, except iPR,	iSD
			iCR	iCR	iCR	
Example 5	iUPD	Any (no iCPD)	iUPD	iCPD	NA	iCPD
Example 6	iUPD	iUPD (no iCPD)	iCPD	NA	NA	iCPD
Example 7	iUPD	iCPD				iCPD
			NA	NA	NA	

iBOR=best overall response; iCR=complete response; iCPD=confirmed progression; iPR=partial response; iSD=stable disease; iUPD=unconfirmed progression; NA=not applicable; NE=not evaluable; RECIST=Response Evaluation Criteria in Solid Tumors.

Note: Prefix "i" indicates immune responses assigned using iRECIST; others without "i" are confirmed by RECIST v1.1.

Adapted from Seymore et al., 2017

If progression is confirmed, the overall response will be iCPD. iCPD is present if any of the factors that were the basis for the initial iUPD show worsening, e.g., ANY of the following occurs:

- For target lesions, worsening is a further increase in the sum of diameters of ≥5 mm, compared to any prior iUPD time point.
- For non-target lesions, worsening is any relevant growth in lesions overall, compared to a prior iUPD time point; this does not have to meet the "unequivocal" standard of RECIST v1.1.
- For new lesions, worsening is any of these:
  - An increase in the new lesion sum of diameters by  $\geq 5$  mm from a prior iUPD time point
  - Visible growth of new non-target lesions
  - The appearance of additional new lesions
  - Any new factor appears that would have triggered PD by RECIST v1.1

NOTE: If a patient has iCPD as defined above, but is achieving a clinically meaningful benefit, an exception to continue study treatment may be considered following consultation with the sponsor. In this case, if study treatment is continued, tumor imaging should continue following the intervals as outlined in the SoA (Table 1) and submitted to the central imaging vendor.

#### Persistent iUPD

If progression is not confirmed, the overall response remains iUPD. iUPD is present if:

• None of the progression-confirming factors identified above occurs AND

• The target lesion sum of diameters (initial target lesions) remains above the initial PD threshold (by RECIST v1.1).

#### Resolution of iUPD

Progression is considered not confirmed, and the overall response becomes iSD/iPR/iCR, if:

- None of the progression-confirming factors identified above occurs, AND
- The target lesion sum of diameters (initial target lesions) is not above the initial PD threshold.

The response is classified as iSD or iPR (depending on the sum of diameters of the target lesions), or iCR if all lesions resolve.

In this case (iSD, iPR, or iCR could be assigned), the initial iUPD is considered to be pseudo progression, and the level of suspicion for progression is 'reset'. This means that the next visit that shows radiographic progression, whenever it occurs, is again classified as iUPD by iRECIST, and the confirmation process is repeated before a response of iCPD- can be assigned.

Detection of Progression at Visits After Pseudo-progression Resolves

After resolution of pseudo-progression (i.e., achievement of iSD/iPR/iCR), iUPD is indicated by any of the following events:

